### **Strong CYP3A4 inhibitors**

Boceprevir, cobicistat, conivaptan, danoprevir and ritonavir, elvitegravir and ritonavir, indinavir and ritonavir, itraconazole, ketoconazole, lopinavir and ritonavir, paritaprevir and ritonavir and (ombitasvir and/or dasabuvir), posaconazole, ritonavir, saquinavir and ritonavir, telaprevir, tipranavir and ritonavir, troleandomycin, voriconazole, clarithromycin, nefazodone, neflifinavir, tacrolimus, mifepristone, mibefradil.

### **Moderate CYP3A4 inhibitors**

Amprenavir, aprepitant, casopitant, cimetidine, ciprofloxacin, diltiazem, dronedarone, erythromycin, fluconazole, grapefruit juice, Seville orange, isavuconazole, lefamulin, letermovir, netupitant, rauconazole, verapamil

The following medications and supplements are some of the moderate to strong inducers of CYP3A4. As described in the study protocol, concomitant use of moderate to strong CYP3A4 inducers is prohibited. This list should not be considered all-inclusive. Individual product labels should be reviewed for specific information on propensity to induce CYP3A4 for a specific compound.

### **Strong CYP3A4 inducers**

Carbamazepine, phenytoin, rifampin, St. John's Wort, rifapentine, phenytoin, phenobarbital, apalutamide

### **Moderate CYP3A4 inducers**

Bosentan, rifabutin, modafinil, nafcillin, efavirenz, etravirine, lopinavir

As described in the study protocol, concomitant use of strong P-gp inhibitors is prohibited.

**Strong P-gp Inhibitors**

Amiodarone, clarithromycin, cyclosporine, dronedarone, itraconazole, lapatinib, propafenone, quinidine, ritonavir, verapamil

Resources:

<https://www.fda.gov/Drugs/DevelopmentApprovalProcess/DevelopmentResources/DrugInteractionsLabeling/ucm093664.htm#table3-2>

<https://www.fda.gov/Drugs/DevelopmentApprovalProcess/DevelopmentResources/DrugInteractionsLabeling/ucm093664.htm#table3-3>

University of Washington Metabolism and Transport Drug Interaction Database accessible at  
<https://www.druginteractioninfo.org/>

eDISH	Evaluation of drug-induced serious hepatotoxicity
eGFR	Estimated glomerular filtration rate
GGT	Gamma-glutamyl transferase
HbA1C	Hemoglobin A1C
HDL	High-density lipoprotein
IR	Immediate release
IWRS	Interactive Web-based Response System
LDL	Low-density lipoprotein
LFT	Liver function test
LSMeans	Least square means
MDRD	Modification of diet in renal disease
MedDRA	Medical Dictionary for Regulatory Activities
mg	Milligram
mITT	Modified Intent to Treat
MMRM	Mixed-effect Model for Repeated Measures
NPRS	Numeric Pain Rating Scale
OLE	Open-label extension
Penn-FPS-R	Penn Facial Pain Scale-Revised
PGI-C	Patient Global Impression of Change Scale
PI	Principal Investigator
PID	Patient Identification Number

Abbreviation	Definition
PT	Prefened telm
QD	Once Daily
SAE	Serious Adverse Event
SAP	Statistical analvsis plan
SD	Standard deviation
SE	Standard enor
SI	Svsteme Internationale
SOC	System Organ Class
S-STS	Sheehan Suicidality Tracking Scale
T4	Thyroxine
TBL	Total bilirubin
TEAE	Treatment-Emergent Adverse Events
TLF	Tables, listings, and fomres
TN	Trigeminal Nemalgia
TSH	Thyroid stimulating honnone
ULN	Upper Limit ofNormal
US	United States
WHO	World Health Organization

1 BACKGROUND AND RATIONALE

This document presents the statistical analysis plan (SAP) for Pfizer Inc. Protocol: BHV3000-202: Phase 2: A Double-Blind, Placebo Controlled, Crossover Trial of BHV-3000 (Rimegepant) for Treatment Refractory Trigeminal Neuralgia (TN).

This SAP is based on the final protocol version 9.0 dated April 8, 2022. It contains the analysis details and methodology to address the study objectives, including planned summary tables, by-subject listings, and figures, which will provide the basis for the results section of the clinical study report (CSR). Operational aspects related to collection and timing of planned clinical assessments are not repeated in this SAP unless relevant to the planned analyses.

The Rimegepant (BHV3000) Core SAP describes analysis details and methodologies common to the BHV3000 program and is incorporated by reference. The Core SAP assumes primacy for any matter where this SAP is silent (and the relevant content of the Core SAP could feasibly apply) or where the Core SAP is directly referenced as applicable. Otherwise, should any discrepancy exist between the Core SAP and this SAP, this SAP assumes primacy.

Note that the study was terminated prematurely in 1Q2023 due to low enrollment. As a result, only critical data would be analyzed for the CSR.

1.1 Research Hypothesis

Rimegepant is superior to placebo in providing symptom relief for treatment-refractory patients with classical or idiopathic trigeminal neuralgia.

1.2 Schedule of Analyses

The final analysis of the Double-blind Treatment (DBT) Phase will occur after the last subject randomized has completed this phase of the study or discontinues from the DBT Phase. The study will be unblinded and analyses will summarize all efficacy, safety, laboratory and other data collected throughout the DBT phase of study.

A final analysis of the study will be completed after the last subject has completed their last study visit of the Open-Label Extension (OLE) Phase of the study. These analyses will summarize all efficacy, safety, laboratory and other data collected throughout the OLE Phase of the study. In addition throughout the study, data may be locked, analyses conducted, and reports produced as required to support safety monitoring or regulatory requirements.

[figure not shown]
[figure not shown]
2 STUDY DESCRIPTION

2.1 Study Design

BHV3000-202 is a phase 2, multi-center, double-blind, placebo controlled, crossover trial to assess the safety, tolerability, and efficacy of rimegepant in treating TN in patients who failed to respond adequately to or had intolerance or a contraindication to pharmacotherapy. Current inadequate response to therapy is defined by a daily pain score of greater than or equal to 4 on the “average intensity” on 11-point Numerical Pain Rating Scale (NPRS) during the 14 days prior to baseline. A crossover design with a placebo washout period of 7 days between treatments will be used due to the limited number of subjects, with each patient serving as their own control. The study will be conducted at multiple centers.

Figure 1 displays the study design.

Figure 1: Study Schematic

Prior to randomization, patients will enter a 14 to 30 day screening period during which they will complete daily self-reported assessments of pain intensity over a 24 hour period using an 11 point NPRS, ranging from 0 (for no pain) to 10 (for the worst imaginable pain). Throughout the

study, patients will be allowed to remain on their current medication regimens, provided they have been on a stable dose for a minimum of 4 weeks prior to the randomization visit.

Patients with a mean of ≥ 4 on the daily “average intensity” on the 11 point NPRS, during the last 14 days of the screening period, will be randomized to one of two treatment sequences to receive rimegepant 75 mg immediate release (IR) tablet administered orally vs placebo. Each sequence will include a 2-week treatment phase, with daily dosing of study drug or placebo. This will be followed by a 7-day placebo washout period. After the placebo washout period, another 2-week treatment phase will follow, again with once daily dosing of study drug or placebo. In the first sequence, patients will receive placebo for the first treatment period and rimegepant 75 mg IR tablet during the second treatment period. The second sequence will receive rimegepant 75 mg IR tablet during the first 2 week treatment period, followed by placebo in the second treatment phase.

During each 2 week treatment phase and during the 7 day placebo washout period, patients will complete the 11 point NPRS daily, as described above. In addition, patients will complete a paper diary daily to record efficacy data. The diary will include the daily recording of overall pain using the 11 point NPRS, a recording of daily use of rescue medications, and a daily rating of worst pain episode using the 11 point NPRS. Other secondary endpoints will be assessed at the beginning and end of each treatment period, including the Penn Facial Pain Scale (a 12-item activities of daily living scale designed specifically to assess impact of TN symptoms on daily activities), the Pain Disability Index (which measures the degree to which chronic pain interferes with 7 categories of daily activities, measured on an 11 point scale ranging from 0 (no disability) to 10 (worst disability)). The Patient Global Impression of Change (PGI-C: a patient self-reported global index scale) will be assessed at the end of each treatment sequence. In addition, the Sheehan-Suicidality Tracking Scale (S-STS) will be administered as a safety measure at screening, as well as at every visit, as specified in the protocol.

In addition, subjects completing the DBT Phase of the study and who continue to meet inclusion/exclusion criteria may be offered up to 12 weeks of OLE treatment, provided the Principal Investigator (PI) believes open-label treatment offers an acceptable risk-benefit profile. Subjects who agree to enter the OLE Phase will not be required to have a wash-out period of drug, but instead should continue dosing as specified in the OLE Phase.

All subjects will undergo a post study Follow-up Safety Visit 14 days after the final EOT Visit and last dose of study drug/medication administration. Subjects who discontinue from the study at any time during either the DBT Phase or the OLE Phase are expected to complete the End of Treatment (day 119) Visit and the 2-Week Follow-up Safety Visit.

2.2 Treatment Assignment

Approximately 120 patients will be screened to randomize 60 patients in a 1:1 ratio into 2 treatment sequences receiving 75 mg rimegepant vs placebo, using a 2-period, 2-sequence, crossover design. Patients with atypical TN and typical TN will be stratified equally into each of the two treatment sequences, with atypical TN patients not exceeding 50 percent of the subjects. Treatment assignments will be obtained by the investigator (or designee) via the Interactive Web-based Response System (IWRS).

2.3 Blinding and Unblinding

This study is blinded to study drug active status (rimegepant vs placebo) through the final analysis of the DBT Phase (see Section 1.2). Draft TLFs are produced with dummy treatment groups prior to the DBT Phase database lock. TLFs for the DBT Phase and subsequent database locks are produced unblinded.

2.4 Protocol and Protocol Amendments

BHV3000-202 SAP Version 2.0 is based on BHV3000-202 Protocol Version 9.0 (08-Apr-2022).

3 STUDY OBJECTIVES AND ESTIMANDS

3.1 Objectives

3.1.1 Primary Objective

To evaluate the efficacy of rimegepant compared to placebo in providing symptomatic pain relief in patients with refractory TN, defined as a reduction from baseline in the average daily NPRS between the two-week treatment phases.

3.1.2 Secondary Objectives

1. To assess the safety and tolerability of rimegepant relative to placebo in patients with TN
2. To evaluate the efficacy of rimegepant vs placebo for improving physical function in TN patients as measured by the Penn Facial Pain Scale-Revised (Penn-FPS-R)
3. To evaluate the efficacy of rimegepant vs placebo for improving functional disability in TN patients as measured by the Pain Disability Index
4. To evaluate the efficacy of rimegepant vs placebo on global functioning as measured by the PGI-C
5. To evaluate the efficacy of rimegepant vs placebo in providing symptomatic pain relief as captured by daily rating of worst pain episode as measured by the 11 point NPRS
6. To evaluate the efficacy of rimegepant vs placebo in providing symptomatic pain relief of clinical importance as defined by a 2-point or greater reduction in the 11 point NPRS

CCI [REDACTED]

[REDACTED]

[REDACTED]

[REDACTED]

3.2 Estimands

An estimand is the target of estimation to address the scientific question of interest posed by a study objective. The 4 attributes of an estimand include the population of interest, endpoint of interest, specification of how intercurrent events are reflected in the scientific question of interest, and the summary for the endpoint.

For all objectives, the population of interest is defined through appropriate inclusion/exclusion criteria to reflect the targeted patient population for approval. Refer to the protocol for inclusion/exclusion criteria.

Intercurrent Events

Intercurrent events are those that occur after treatment initiation and either preclude observation of the endpoint or affect its interpretation. The following will be considered intercurrent events:

- Study drug discontinuation before the time point of interest defining the endpoint.
 - For safety objectives:
 - For AEs, study drug discontinuation is handled with a “while-on-treatment strategy,” i.e., response to treatment prior to the occurrence of the intercurrent event of interest, such that all observed values of the endpoint of interest will be used prior to study drug discontinuation.
 - For all other safety endpoints, study drug discontinuation is handled with a “treatment policy strategy”, i.e., the occurrence of the intercurrent event will be considered irrelevant, such that all observed values of the endpoint of interest will be used regardless of study drug discontinuation.
 - For efficacy objectives:
 - For the NPRS objectives, study drug discontinuation is handled with a “while-on-treatment strategy”.
 - For the Penn-FPS-R, PDI, and PGI-C efficacy objectives, study drug discontinuation is handled with a “treatment policy strategy”.
 - For all other objectives (i.e., use of non-study TN standard of care medications on or before the time point of interest), this intercurrent event will be handled with a “while-on-treatment strategy”

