#### **4.4.1 Trigeminal Neuralgia Medications**

Throughout the study, patients will be permitted to use Standard of Care Trigeminal Neuralgia medications, with the exception of carbamazepine, including rescue medications, provided that these medications have been used at stable dosing for at least 4 weeks prior to randomization visit. Use of these concomitant medications will be recorded daily by the subject on a paper diary and reported to the site.

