3.2.1 Primary Objective Estimand

[Table 1](#) presents the estimand for the primary objective.

Table 1: Primary Objective Estimand

Objective	To evaluate the efficacy of rimegepant compared to placebo in providing symptomatic pain relief in patients with refractory TN, defined as a reduction from baseline in the average daily NPRS between the two-week treatment phases.
Efficacy Endpoint	Change from baseline to the average of the 2-week treatment phase of the study in the average daily NPRS
Summary	Using the modified Intent to Treat (mITT) population: 
• Descriptive statistics for the averaged daily NPRS score and change from baseline score as a continuous variable by treatment group at each 2-week treatment phase• Difference in mean change from baseline in average daily NPRS scores between treatment groups estimated using a mixed-effect model for repeated measures (MMRM)
Intercurrent Events	Study drug discontinuation: while-on-treatment strategy

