6.3 Efficacy

Unless otherwise noted, the primary and secondary efficacy analyses will be conducted on the mITT population. DBT and OLE efficacy data will be included in listings by subject, treatment sequence and period, study phase and visit (as applicable). Descriptive summary statistics will be provided for DBT and OLE phase data. Statistical analyses outlined in Table 3: Primary and Secondary Efficacy Estimands and Analyses will only be done for the DBT phase data.

Table 3: Primary and Secondary Efficacy Estimands and Analyses

Index	Description	Variable Type	Statistical Model	On-Study Data
Primary Estimand				
P01	Difference between treatment groups in change from baseline in average daily NPRS scores at the end of the randomization phase	Continuous	MMRM	Baseline, Day 14, 21, 35
Secondary Estimand				
S01	Difference between treatment groups in change from baseline in Penn-FPS-R score at the end of the randomization phase	Continuous	MMRM	Baseline, Day 14, 21, 35
S02	Difference between treatment groups in change from baseline in Pain Disability Index at the end of the randomization phase	Continuous	MMRM	Baseline, Day 14, 21, 35
S03	Difference between treatment groups in PGI-C at the end of the randomization phase	Continuous	MMRM	Day 14, 21, 35
S04	Difference between treatment groups in change from baseline in worst pain episode measured by NPRS at the end of the randomization phase	Continuous	MMRM	Baseline, Day 14, 21, 35
S05	Difference between treatment groups in percentages of subjects with ≥ 2 point reduction from baseline in average daily NPRS score	Binary	Logistic Regression	Baseline, Day 14, 21, 35

MMRM = Mixed effects model for repeated measures

6.3.1 *Continuous Efficacy Endpoints*

Assessments are taken directly from reported CRF visits, aside from the NPRS endpoints which are only taken between treatment exposure start and end dates.

Descriptive Analyses

Summary statistics for parameter values are tabulated at select time points by treatment group (rimegepant pooled or placebo pooled).

MMRM

Treatment groups are assessed using MMRM with the following variables:

- Dependent variable: change from baseline of NPRS score averaged over each DBT period
- Fixed effects (categorical variables): treatment group, sequence, and period
- Covariate (continuous variable): baseline value of dependent variable

Random effect: subject error degrees of freedom are determined by the Kenward-Roger method.

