Subjects were given a paper diary to record daily pain intensity on the NPRS. They were asked to keep a daily record of their average pain intensity over a 24 hour period.

The primary endpoint is the change in average daily NPRS from baseline to the end of the 2-week treatment phase of the study. Pain relief is defined as an improvement (reduction) from baseline. The primary endpoint will estimate the effect of rimegepant relative to placebo over 2 weeks of treatment when added to a standard of care therapy, and regardless of the effect of other concomitant medication. The pain score will be the average of the daily 11-point NPRS recorded within each period using the mITT population. This treatment effect will be

summarized as the difference in the average daily score in total NPRS between rimegepant and placebo.

The primary endpoint will be analyzed using the method specified in Section 6.3.1. The MMRM table has the same format as the one described in Section 6.3.1.

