 - IWRS randomization stratum of "typical", but CRF Neuralgia type "atypical" (Demographics page)
- Prohibited non-study medications, procedures, or therapies defined as any of the following:
 - Standard of care Trigeminal Neuralgia medications with dose change or with start date < 4 weeks prior to randomization (see Section 4.4.1 for the definition of standard of care Trigeminal Neuralgia medication)
 - Carbamazepine taken during the Screening Period or afterward

- St. John's Wort taken up to 14 days prior to the Baseline Visit (randomization) or afterward
- Barbiturate-containing products (e.g. Fioricet, Fiorinal, butalbital, phenobarbital) taken up to 14 days prior to the Baseline Visit (randomization) or afterward
- Modafinil (PROVIGIL®) taken up to 14 days prior to the Baseline Visit (randomization) or afterward
- Butterbur root or extracts taken up to 14 days prior to the Baseline Visit (randomization) or afterward
- Ergotamine medications taken on ≥ 10 days per month on a regular basis for ≥ 3 months
- Narcotic medication, such as opioids, taken up to 2 days prior to the Baseline Visit or afterward
- Acetaminophen or acetaminophen containing products taken within 2 days before randomization.
- Use of acetaminophen during the Screening Period (3 to 14 days) or throughout the study at daily dosing levels of greater than 1000 mg/day
- Muscle relaxants (except baclofen) taken during the Screening Period or throughout the study
- Baclofen with start date < 8 weeks prior to randomization
- Strong CYP3A4 inhibitors taken during the Screening Period or throughout the study
- Strong CYP3A4 inducers taken during the Screening Period or throughout the study
- Strong inhibitors of the P-gp transporter taken during the Screening Period or throughout the study
- CGRP antagonists (biologic or small molecule) taken during the Screening Period or throughout the study

Note: Medications taken up to X days before a reference date or afterward are defined as those with medication start date or stop date \geq reference date $- X$. Refer to the Core SAP for additional details about prohibited non-study medications.

- DB study drug dosing issue, defined as any of the following subcategories (see Section 6.2.6):
 - DB study drug taken but not randomized
 - DB tablet count compliance < 80% from DB study drug start to later of last scheduled DBT Phase visit or DB study drug end
 - > 1 DB tablet taken on any 1 day
 - Incorrect DB study drug taken

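### Do the unclear last intercurrent-event bullet in SAP 3.2 and the time points in SAP Table 3 change what the trial estimates?

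*SAP*

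**What the plan says.** **Intercurrent events.** SAP 3.2 opens its list with "The following will be considered intercurrent events", in the plural, but sets out one event: stopping study drug. Strategies follow by objective. They are while-on-treatment for AEs and the NPRS endpoints, and treatment policy for other safety endpoints, Penn-FPS-R, PDI and PGI-C. The last line is addressed to all remaining objectives, yet its parenthesis describes an event: "use of non-study TN standard of care medications on or before the time point of interest), this intercurrent event will be handled with a" (the strategy named is while-on-treatment). Table 1 has a single entry for the primary estimand, "Study drug discontinuation: while-on-treatment strategy", and Table 2 likewise lists only discontinuation.

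Elsewhere, SAP 6.3.4.1 repeats Protocol 9.4.2 and defines the primary effect as that of rimegepant "when added to a standard of care therapy, and regardless of the effect of other concomitant medication". SAP 6.3.1 and 6.3.3 take assessments as recorded at CRF visits, "aside from the NPRS endpoints which are only taken between treatment exposure start and end dates". In its list of deviations, SAP 9.1 sends the reader elsewhere for the meaning of background therapy: "see Section 4.4.1 for the definition of standard of care Trigeminal Neuralgia medication".

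**Time points.** Table 3 places P01 and S01 to S04 at the close of the randomization phase, which Protocol 3.5.2 gives as 35 days. Its On-Study Data column shows Days 14, 21 and 35 in every row. Tables 1 and 2 speak instead of the 2-week treatment phase.

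**The concern.** Medication use is part of everyday life in this trial. Protocol 4.4.1 lets patients keep stable standard-of-care TN drugs "with the exception of carbamazepine, including rescue medications". If the last line of SAP 3.2 were a general rule for that event, pain scores recorded after such use would fall outside the estimand. That would contradict the effect stated in Protocol 9.4.2.

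Table 3 raises a similar worry, because SAP 6.3 names it as the outline of the statistical analyses. A comparison dated to Day 35 would see each patient on one treatment only and give up the crossover. If Day 21 entered the comparison, placebo-washout data would be mixed into it.

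With no significance test planned, the estimates and intervals are the efficacy result, so it matters that a reader can tell what they estimate.

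**Working it through.** The plan's one related figure is its power. Completers: 60 × 0.8 = 48. Standard error: 3.8/√48 = 0.548. Ratio: 2/0.548 = 3.65. The paired t-test then has 94.6% power, which agrees with the stated value above 90%. Nothing in this concern enters that calculation, so the rest is a comparison of passages.

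**1. Medication use.** There are six visible efficacy estimand rows: Table 1 (1) plus Table 2 Objectives 2 to 6 (5). None lists medication use. The handling for NPRS can still be read from two other places. SAP 6.3.4.1 sets the effect regardless of other medication, and 6.3.1, 6.3.3 and 7.2 restrict NPRS scores by exposure dates and nothing else. For Penn-FPS-R, PDI and PGI-C, 6.3.1 and 6.3.2 use the CRF visits with no exclusion for medication. No data rule removes a score because a TN drug was taken.

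The general-rule reading also defeats itself. Background TN therapy is allowed throughout, so a patient on it has used such medication from the first day. Taken literally, the rule would leave that patient with no usable scores in a trial of add-on treatment.

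If the line is instead read as the residual category it claims to be, it does not reach NPRS, Penn-FPS-R, PDI or PGI-C, which all have their own lines. It may then refer to objectives blacked out directly after the secondary list in SAP 3.1.2, or after Table 2.

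**2. Cross-reference.** SAP section 4 has only 4.1 and 4.2, so the pointer in 9.1 can only sensibly mean Protocol 4.4.1. SAP 6.2.6.3 separately defines rescue medication by its own CRF.

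**3. Table 3 against the operative text.**

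| Row | Table 3 time point | Tables 1 and 2 | Rule that governs |
|---|---|---|---|
| P01 | close of 35-day phase | average over 2-week period | 6.3.1 (period average); 7.2 |
| S04 | same | average over 2-week period | 6.3.5.4, as primary; 7.2 |
| S01, S02 | same | end of 2-week period | 7.2 |
| S03 | same | end of 2-week period | 6.3.2 (Day 14 of each period); 7.2 |
| S05 | none | none | 6.3.3; 7.2 |

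Two rows (P01, S04) differ from both the estimand tables and 6.3.1. Three rows (S01 to S03) repeat the wording of Protocol 3.2 and differ only within the SAP. One row (S05) states no time point: 2 + 3 + 1 = 6. In every row, 7.2 assigns period 1 to Day 14 and period 2 to Day 35.

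**4. Could Day 35 alone be analysed?** Not with the stated model. SAP 6.3.1 fits treatment, sequence and period. With one record per patient at Day 35, period has a single level and treatment is fixed by sequence, so the treatment effect cannot be separated from sequence. The P01 row itself lists Day 14 beside Day 35 under MMRM.

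**5. Could Day 21 enter the comparison?** SAP 7.2 gives it no efficacy period. The washout is dosed with placebo, so exposure dates alone might leave doubt, but 7.2 ties NPRS period 1 to the Day 14 visit. The AE window in 6.4.1.3 does run to the Day 21 dose, but 7.2 confines that rule to AEs. Day 21 is a scheduled visit, and Table 2 plans descriptive statistics at each visit for Objectives 2 to 4, so listing it as on-study data is not shown to be an error.

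**The case for a change.** The strongest case for a change is that section 3.2 and Table 3 are where a reader looks for the estimand, and each can be read in a way that does not give the protocol's effect. An objective is not an event, and redaction does not repair a parenthesis that equates the two. Nor can the Core SAP be assumed to settle it. SAP section 1 says "The Core SAP assumes primacy for any matter where this SAP is silent", but on this point the SAP is unclear rather than silent. Version 2.0 also revised the strategies in 3.2, so the passage was meant to be read.

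Most of this stands as a comment on drafting. The bullet's scope cannot be determined from the visible text, the time point for P01 and S04 is mislabelled, and the pointer in 9.1 lacks the word Protocol.

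What does not stand is any consequence for the analysis. The clash over medication needs one optional reading of a line whose context is partly redacted. The Day 35 and washout readings are excluded by the plan's own model and period definitions. Calculations of lost precision or a diluted effect under those readings would describe analyses that nobody has planned, so they do not measure the size of this point.

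**Conclusion.** No change to the plan follows. These are clerical slips, plus one line of unclear scope, in text that summarises the analysis. The sections that direct the programming are explicit and agree with the protocol's primary effect. Following 6.3.1 to 6.3.3, 6.3.4.1 and 7.2 gives the intended treatment comparison, with no pain score excluded for medication use and no washout visit in the model. The effect on estimates and confidence intervals is nil, and SAP section 5 evaluates no significance. SAP section 1 adds that the study stopped early for low enrollment and that only critical data are analysed, which leaves still less to gain from redrafting.

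This rests on two assumptions: that analysts apply the detailed rules over the summary labels, and that neither the redacted objectives nor the Core SAP, which are not visible here, imposes a medication-use rule on the NPRS endpoints. Such a rule would contradict SAP 6.3.4.1, and this SAP takes precedence over the Core SAP where the two differ.
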